### 6.4 Prior and Concomitant Therapy

All medications administered and procedures conducted within 28 days before C1D1 should be recorded on the eCRF. In addition, all prior treatments for the underlying malignancy should be recorded.

### 6.4.1 Prohibited Concomitant Therapy

The following medications and procedures are prohibited during the study:

- In vitro studies with recombinant human CYP enzymes demonstrated that avapritinib phase I metabolism is predominantly mediated by CYP3A4, with CYP2C9 playing a minor role. Concomitant treatment with drugs that are strong CYP3A4 inhibitors or strong or moderate CYP3A4 inducers are prohibited for patients receiving avapritinib. Please refer to [Appendix 3](#) for a list of prohibited medications and foods.
- Regorafenib is metabolized by CYP3A4 and UGT1A9. Concomitant treatment with drugs that are strong inhibitors of CYP3A4, strong inducers of CYP3A4, and strong inhibitors of UGT1A9 are prohibited for patients receiving regorafenib. Please refer to [Appendix 3](#) for a list of prohibited medications and foods.
- Any investigational agent or device other than avapritinib or regorafenib, including commercially available agents that are investigational for the treatment of the patient's underlying malignancy.
- Any antineoplastic treatment (including kinase inhibitors, chemotherapy, and radiotherapy) other than avapritinib and regorafenib. Patients who experience centrally confirmed disease progression but subsequently undergo radiation therapy or surgery may continue to receive study treatment with avapritinib, if the treating investigator considers it to be in the patient's best medical interest.

### 6.4.2 Concomitant Therapy to be used with Caution

#### Avapritinib

In vitro, avapritinib is a reversible inhibitor of CYP2C9, and CYP3A4/5 at clinically relevant concentrations. Avapritinib also demonstrated time-dependent inhibition of CYP3A4/5 in vitro with an estimated  $K_{inact}$  and  $K_I$  of  $0.0301 \text{ min}^{-1}$  and  $12.3 \text{ }\mu\text{M}$ , respectively. Therefore, avapritinib treatment may increase the plasma concentration of other medications for which CYP2C9 or CYP3A-mediated metabolism constitutes the primary mechanism of clearance.

In vitro, avapritinib, at concentrations of 0.3 to 3  $\mu\text{M}$ , induced CYP3A4 mRNA expression with a maximal 3.25-fold induction observed at 3  $\mu\text{M}$ . In vitro, avapritinib is an inhibitor of P-gp, BCRP, BSEP, and MATE1 and MATE2K. Therefore, avapritinib may increase the plasma concentration of other medications that are substrates of these transporters. Medications that are CYP2C9, CYP3A4 or BCRP substrates, with a narrow therapeutic index and moderate inhibitors of CYP3A4 should be used with caution (Refer to [Appendix 4](#) for a list of these medications).

Investigators should ensure patients avoid proton pump inhibitors and H2-receptor antagonists during the study. Furthermore, antacids should be taken at a time point that is not proximal to study drug administration (at least 3-4 hours before or after study drug administration).

In addition, medications that are known to increase the risk of seizures should be used with caution.

### **Regorafenib**

Investigators should ensure patients exercise caution while using concomitant therapies with regorafenib as listed in [Appendix 4](#).

#### **6.4.3 Permitted Concomitant Therapy**

Medications and treatments other than those specified in [Section 6.4.1](#) and [Section 6.4.2](#), including palliative and supportive care for disease-related symptoms are permitted during the study.

[figure not shown]

Patients should be closely monitored, and treatment is to be instituted for disease-related symptoms as appropriate. Supportive care measures for treating AEs should be instituted as soon as they are recognized.

Anti-emetic treatments may be used at the Investigator's discretion and in accordance with the American Society of Clinical Oncology guidelines or equivalent after documented nausea or vomiting has occurred without medications having been used. The choice of anti-emetic treatment, if required, will be made at the Investigator's discretion. Anti-diarrhea medications may also be used after documented diarrhea has occurred, at the Investigator's discretion.

## 6.5 Schedule of Assessments

**Table 2: Schedule of Assessments**

Study Activities a	Screening	Study Treatment						EOT e ± 7 days	Safety Follow- Up f ± 7 days	PFS Follow-up g ± 7 days	Survival Follow- up h ± 30 days
		C1		C2 ± 2 days		C3, C4, C5 b,c ± 3 days	C7-EOT b,d ± 7 days				
Cycle											
Study Day	-28 to -1	D1	D15	D1	D15	D1	D1	14 days after last dose	30 days after last dose	Every 8 weeks after Safety F/U	Every 2 months
Window (Days)						±3	±7	±7	±7	±7	±1 month
Informed consent i	X										
Inclusion/exclusion criteria	X										
Demographics	X										
Medical history j	X										
Physical examination k	X	X		X		X	X	X			
Vital signs l	X	X	X	X	X	X	X	X			
Serum or urine pregnancy m (β-hCG) test	X	X		X		X	X	X	X m		
ECOG PS	X	X		X		X	X	X			
12-lead ECG	X	X		X		X	X	X			
Hematology n	X	X o		X		X	X	X			
Coagulation p	X	X o						X			
Serum chemistry q	X	X o	X r	X	X r	X	X s	X			

Study Activities a	Screening	Study Treatment						EOT e ± 7 days	Safety Follow-Up f ± 7 days	PFS Follow-up g ± 7 days	Survival Follow-up h ± 30 days
		C1		C2 ± 2 days		C3, C4, C5 b,c ± 3 days	C7-EOT b,d ± 7 days				
Cycle											
Study Day	-28 to -1	D1	D15	D1	D15	D1	D1	14 days after last dose	30 days after last dose	Every 8 weeks after Safety F/U	Every 2 months
Window (Days)						±3	±7	±7	±7	±7	±1 month
Urinalysis	X	X o						X			
Study drug administration		X									
PK blood samples c (Arm A: avapritinib patients only)		X		X		X c					
Mutation screening (ctDNA sample)	X										
Plasma sample for biomarkers		X o		X		X	X	X			
Tumor imaging t	X					X t	X	X		X	
Brain imaging (MRI or CT) u	X					X	X				
EORTC-QLQ-C30,    		X		X		X v	X v				
AE monitoring w		X									
SAE monitoring x		X									
Concomitant medications x		X									
Survival assessment											X
New antineoplastic therapy											X

- Abbreviations: AE = adverse event; C = cycle; CT = computed tomography; ctDNA = circulating tumor deoxyribonucleic acid; D = day; ECG = electrocardiogram; ECOG PS = Eastern Cooperative Oncology Group Performance Status; EORTC-QLQ-C30 = European Organisation for Research and Treatment of Cancer Quality of Life Questionnaire; EOT = End-of-Treatment; EQ-5D-5L = EuroQol 5 Dimension Questionnaire; F/U = follow-up; FACT-Cog = Functional Assessment of Cancer Therapy-Cognitive Function; GIST = gastrointestinal stromal tumor; IV = intravenous; MRI = magnetic resonance imaging; PD = progressive disease; PFS = progression-free survival; MRI = magnetic resonance imaging; PGI-C = Patients' Global Impression of Change; PGI-S = Patients' Global Impression of Severity; PK = pharmacokinetics; SAE = serious adverse event; ULN = upper limit of normal.
- a On days when study drug is to be administered in the clinic, all tests or procedures must be completed pre-dose at each study visit unless otherwise indicated. Additional safety tests (eg, hematology, ECG) may be performed whenever clinically indicated, at the Investigator's discretion. Whenever a test result is questionable, it should be repeated immediately.
  - b Patients receiving regorafenib who experience disease progression documented by central radiology review may be permitted to cross over to receive treatment with avapritinib after disease progression confirmed by central radiology review (see [Section 7.6](#)) and a washout period of 7 to 28 days after their last dose of regorafenib. At the first study visit after the washout period, the patient will complete the C1D1 assessment schedule except for the following tests, which are not required: PK blood sample and biomarker plasma sample. After patients cross over to treatment with avapritinib, ECGs will be performed following the same schedule as prior to cross over and AEs will only be assessed for their relationship to avapritinib.
  - c Pharmacokinetics samples will be collected before dosing (ie, predose) on Day 1 of Cycles 1, 2, 3, and 5 only from patients in Arm A of the study (those receiving avapritinib). There will be no PK samples collected from patients in Arm B of the study (those receiving regorafenib). On C3D1 and C5D1, in addition to the predose sample in all patients, samples will be collected at any 1 time point between 1-8 hours postdose. On C2D1, additional samples will be collected predose and at 1 hour ( $\pm 10$  minutes), 4 hours ( $\pm 15$  minutes), and 6-8 hours ( $\pm 15$  minutes) postdose in a total of 25 patients at selected centers. Note: The predose samples for all patients are to be collected before the day's dose of avapritinib and should be taken as close as possible to 24 hours after the prior dose was taken.
  - d Every odd Cycle D1, eg, C7D1, C9D1, etc., moving forward through EOT. Visits may be performed more frequently, if dictated by the local standard of care or if needed to adequately monitor individual patients.
  - e If an alternative antineoplastic treatment is to be started within 14 days after the last dose of study drug, the EOT visit should be conducted before the dose of alternative antineoplastic therapy. Tumor assessment for EOT procedures do not need to be repeated if they were conducted within 7 days (or within 28 days for disease response assessments).
  - f The Safety Follow-up visit may be performed by clinic visit or a phone call for resolution of any ongoing AEs.
  - g After completing the Safety Follow-up assessments, patients are to be followed for tumor imaging every 8 weeks ( $\pm 7$  days) until disease progression, death, initiation of new anti-GIST therapy, withdrawal of consent, or closure of the study by the Sponsor.
  - h After documentation of disease progression by central radiology review, patients or their designated care giver will be contacted by phone every 2 months until withdrawal of consent, death, or closure of the study by the Sponsor to collect the drug name of any new systemic antineoplastic therapy or the date of death.
  - i Patients randomized to Arm A must consent to continue avapritinib treatment after disease progression and patients randomized to Arm B must consent to cross over to avapritinib after disease progression; see [Section 7.7](#) for additional details.
  - j A complete medical history will be obtained at the Screening visit, including a history of GIST and/or other malignancies, prior treatments, response to each treatment (if available), and concurrent illnesses.
  - k A complete physical examination and a basic neurological assessment will be performed at the Screening visit. Subsequent physical examinations will focus on symptoms and signs of GIST, changes from previous physical examinations, and AEs.
  - l Vital signs include weight, temperature, pulse, and systolic/diastolic blood pressure. Height will also be measured at Screening.

- m To be performed for women of childbearing potential. A serum pregnancy test is to be performed at Screening and at C1D1. A serum or urine pregnancy test should be performed every 4 weeks, even if a study visit is not specified, through 8 weeks after the last dose of study drug. Pregnancy tests may be performed locally during even cycles after C5D1  $\pm$  5 days from expected CXD1 (ie, C6D1, C8D1, etc).
- n Hematology parameters to be measured include hemoglobin, red blood cell count, white blood cell count with differential count (including absolute neutrophil count), and platelet count.
- o Baseline (C1D1) safety laboratory tests and samples for pharmacodynamic markers are to be obtained within 7 days before the first study drug dose (prior to dosing on the first day of dosing permitted). If Screening tests occur within 7 days of C1D1, they do not need to be repeated.
- p Coagulation studies include prothrombin time, international normalized ratio and activated partial thromboplastin time.
- q The comprehensive serum chemistry panel includes sodium, potassium, blood urea nitrogen or urea, bicarbonate (venous), creatinine, calcium, chloride, magnesium, phosphorus, albumin, AST, ALT, alkaline phosphatase, and total bilirubin (direct bilirubin if total bilirubin is > ULN).
- r Only liver function tests (ALT, AST, alkaline phosphatase, total bilirubin (direct bilirubin if total is > ULN) are required. These should be performed locally and any clinically significant abnormalities should be reported as an Adverse Event, and the laboratory values supporting Adverse Event should be entered into unscheduled visit laboratory page on eCRF.
- s Liver function tests (ALT, AST, alkaline phosphatase, total bilirubin (direct bilirubin if total is > ULN) should be measured every 4 weeks. On even-numbered cycles, when a study visit is not required, these tests should be done locally, and any clinically significant abnormalities should be entered as adverse events, and laboratory values should be entered in unscheduled laboratory eCRF.
- t Tumor imaging will be done at Screening and then every 8 weeks ( $\pm$  1 week) from Cycle 1 Day 1 until disease progression and will be assessed by central radiology review. Disease response assessments using the Choi criteria will be performed centrally. Note that tumor imaging should occur every 8 weeks regardless of the scheduled treatment cycles ie, if study treatment is interrupted or discontinued for any reason, tumor imaging should continue according to an 8-week schedule until disease progression or death. Computed tomography (CT) with IV contrast of the chest and CT or MRI with IV contrast of the abdomen and pelvis will be performed. CT of the chest is not required after screening unless there were sites of disease in the chest. CT with IV contrast is the preferred imaging modality, unless a site of disease is better evaluated by MRI. If a patient is not tolerant of IV contrast, non-contrast scans may be performed. For each patient, the same method of tumor imaging used at baseline should be used throughout the study.
- u Brain imaging should be performed at Screening, Week 12 ( $\pm$ 1 week), and Week 24 ( $\pm$ 1 week), and should be repeated as clinically indicated, ie, for unexpected neurologic AE. Patients who have been on study for more than 12 weeks should have imaging performed at the next scheduled visit and 12 weeks later ( $\pm$ 1 week).
- v The EORTC-QLQ-C30, [REDACTED] will be completed at scheduled clinical site visits up to EOT. The questionnaires are not required at the EOT visit or after cross-over.
- w Adverse events are to be recorded from the start of study drug administration through the Safety Follow-up Assessment.
- x Serious AEs and concomitant medications are to be recorded from the date of the informed consent signature through the Safety Follow-up Assessment.

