## 7 DESCRIPTION OF STUDY PROCEDURES

### 7.1 Screening

After informed consent, all patients will undergo screening procedures within 28 days before dosing on C1D1 to determine eligibility. Patients may be randomized in the system at any time but must be dosed within 28 days of signing of informed consent.

The following procedures will be performed at the Screening visit:

- Obtain demographic data, including sex, date of birth/age, race, and ethnicity;
- Complete medical history, including a history of GIST and/or other malignancies, prior treatments, the response to each treatment if available, and concurrent illnesses;
- Complete physical examination and a basic neurological assessment, including ECOG PS;
- Vital signs including weight, temperature, pulse, and systolic/diastolic blood pressure. Height will also be measured at Screening;
- 12-lead ECG;
- Obtain plasma sample for exploratory biomarkers and ctDNA mutation testing;
- Clinical laboratory assessment (hematology, coagulation, serum chemistry, and urinalysis);
- Serum pregnancy test (women of childbearing potential only);

- Tumor imaging by CT with IV contrast or MRI (CT is required for the chest and preferred for all body regions unless a site of disease is better imaged by MRI). If a patient is intolerant of IV contrast, CTs may be performed without IV contrast.
- Brain imaging by MRI or CT (MRI is preferred, if available);
- Recording of concomitant medications and SAEs. Concomitant medications and SAEs are to be collected from the date of the informed consent signature through the Safety Follow-up Assessment, while AEs are to be collected from start of study drug administration through the Safety Follow-up Assessment.

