## 7.8 End-of-Treatment, Safety Follow-up and Progression-Free Survival Follow-up

All patients will attend an EOT visit approximately 14 days ( $\pm$  7 days) after the last dose of study drug (see [Table 2](#) for a description of EOT assessments). If an alternative antineoplastic treatment is started within 14 days of the last dose of study drug, the EOT visit should be conducted before the first dose of the alternative antineoplastic therapy. Tumor assessment for EOT procedures do not need to be repeated if they were performed within 7 days (or within 28 days for disease response assessments).

A Safety Follow-up visit (clinic visit or a phone call) for resolution of any ongoing AE will be made 30 days ( $\pm$  7 days) after the last dose of study drug, or at the time the patient initiates another antineoplastic therapy.

Thereafter, patients without documented PD will be followed approximately every 8 weeks ( $\pm 7$  days) until disease progression, death, initiation of new anti-GIST therapy, withdrawal of consent, or closure of the study by the Sponsor.

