#### **9.4 Adverse Event Monitoring Period**

Adverse events will be recorded in the eCRF from the first dose of a study drug dose through 30 days after the last dose of any study drug. Serious AEs and serious pretreatment events (see [Section 9.9](#)) will be recorded in the eCRF from the time of signing informed consent through 30 days after the last study drug dose. In addition, SAEs that are assessed as related to study treatment that occur > 30 days post-treatment will also be reported. All related AEs and AEs relating to cognitive function and intracranial bleeding should be monitored until they are resolved, are stabilized, have returned to pre-exposure baseline, are determined to be due to another illness, or until a subsequent antineoplastic therapy is initiated, even if > 30 days post last dose of study drug. For AEs considered not related to study drug, similar monitoring guidelines will only be required through 30 days after the last dose of study drug.

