#### **4.7.1 Adverse Events**

Adverse Events will be analyzed using treatment-emergent adverse events (TEAEs). The TEAE definition is dependent on the study period (e.g., main study treatment period) reported. An AE is considered a TEAE for a specified study period if the AE occurs during or after administration of the first dose of study drug from the same study period through up to the earlier of the last dose of study drug in that period + 30 days or the day before the start of crossover/extended treatment.

Adverse Event refers to TEAEs unless otherwise specified throughout this document. All AEs will be coded using MedDRA version 18.1. The severity will be graded using the National Cancer Institute (NCI) Common Terminology Criteria for Adverse Events (CTCAE), version 4.03 (patients enrolled before protocol amendment 2) and 5.0.

A patient experiencing multiple AEs under the same PT or SOC will be counted only once for that PT or SOC by maximum severity. If a patient experiences the same AE more than once with more than one causal relationship to study drug, the strongest causal relationship to study drug will be given precedence. Any missing severity, causality, or outcome will not be imputed and classified as 'Missing'. Detailed imputation rules for missing AE dates are in [Section 7.1](#).

The number of patients with at least one AE will be summarized ([Table 4](#)). The following tables summarize incidences of various aspects of AEs and serious adverse events (SAEs):

1. AE Summary (including all subsequent items)
2. AE by PT
3. AE by SOC and PT
4. AE related to study drug by PT
5. AE related to study drug by SOC and PT
6. SAE by PT
7. SAE by SOC and PT
8. SAE related to study drug by PT
9. SAE related to study drug by SOC and PT
10. Grade 3/4/5 AE by PT
11. Grade 3/4/5 AE by SOC and PT
12. Grade 3/4/5 AE related to study drug by PT
13. Grade 3/4/5 AE related to study drug by SOC and PT
14. AE by PT and NCI CTCAE Grade
15. AE by SOC, PT, and NCI CTCAE Grade

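### Table 2 and section 7.1 let AE and concomitant-medication recording end at a Safety Follow-up that can precede day 30, while section 9.4 and the SAP run to 30 days after last dose

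*Protocol*

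**What the plan says.** The protocol gives two ends for the same data.

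**Visit-based end.** Table 2 note w: "Adverse events are to be recorded from the start of study drug administration through the Safety Follow-up Assessment". Note x: "Serious AEs and concomitant medications are to be recorded from the date of the informed consent signature through the Safety Follow-up Assessment". Section 7.1 repeats the rule for non-serious AEs: "AEs are to be collected from start of study drug administration through the Safety Follow-up Assessment". Section 7.8 sets the timing of that visit: "A Safety Follow-up visit (clinic visit or a phone call) for resolution of any ongoing AE will be made 30 days", with a window of 7 days either side, "or at the time the patient initiates another antineoplastic therapy". Section 4.1 has the same two triggers. Neither section sets a minimum day for the second one.

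**Fixed end.** Section 9.4: "Adverse events will be recorded in the eCRF from the first dose of a study drug dose through 30 days after the last dose". It gives SAEs the same end, and related SAEs remain reportable beyond it. Section 7.2.7 uses 30 days for AEs, SAEs and concomitant medications.

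**Analysis window.** Protocol section 10.5.4.1 counts AEs to 30 days after last dose. SAP section 4.7.1 counts a TEAE "through up to the earlier of the last dose of study drug in that period + 30 days" or the day before crossover or extended treatment starts. SAP section 4.4.1 (concomitant medications) and section 4.7.4 (on-treatment deaths) also use last dose plus 30 days.

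**The concern.** The safety tables rest on a 30-day tail after the last dose. If collection can stop earlier than that for some patients, the tables count a window that was not fully observed, and nothing in the output shows it. The patients affected are those with an early Safety Follow-up, in particular those who move quickly to an off-study drug. The SAP cuts its TEAE window at crossover or extended treatment but not at the start of off-study therapy, which is the event that brings the Safety Follow-up forward. A site can comply with Table 2 and still fall short of section 9.4.

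**Working it through.** No figure in the plan bears on this, so there is none to reproduce. The check has two parts: whether anything later closes the gap, and how wide the gap is.

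**1. Does a later contact collect new AEs?** Take a patient who leaves for an off-study drug and has the Safety Follow-up at that point.
- Section 9.5 has patients questioned about AEs at each visit, so elicitation depends on a visit taking place.
- PFS follow-up is for tumor imaging and ends when new anti-GIST therapy starts (Table 2 note g, section 7.8).
- Survival calls come every 2 months and collect the name of a new drug or the date of death (note h, section 7.9).
- Extended monitoring under sections 9.4 and 9.8.1 follows related, cognitive and intracranial-bleeding AEs, but ends when subsequent therapy starts.

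No scheduled contact elicits new AEs between the early Safety Follow-up and day 30. Early switching is foreseen: section 7.8 and Table 2 note e make provision for alternative antineoplastic treatment within 14 days of last dose.

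**2. Width of the gap.** Inputs: a 30-day window (section 9.4, SAP section 4.7.1) and a visit at 30 ± 7 days (section 7.8), that is, days 23 to 37. For a last contact on day *d*:

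- uncovered days = max(0, 30 − *d*)
- share of the post-dose window = uncovered days / 30
- share of the patient's TEAE window = uncovered days / (*T* + 30), where *T* is days on treatment.

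The documents do not give *T*, so three values are assumed: 28 (one cycle); 152 (the planning median PFS for regorafenib, 5 × 30.4375); and 227 (that median divided by the planning hazard ratio, 5 / 0.67 × 30.4375). Days 14 and 7 are illustrations of an early switch.

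| Last contact | Uncovered days | Share of 30 days | *T* = 28 | *T* = 152 | *T* = 227 |
|---|---|---|---|---|---|
| Day 30 to 37 | 0 | 0% | 0% | 0% | 0% |
| Day 23 | 7 | 23% | 12.1% | 3.8% | 2.7% |
| Day 14 | 16 | 53% | 27.6% | 8.8% | 6.2% |
| Day 7 | 23 | 77% | 39.7% | 12.6% | 8.9% |

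For example, 7 / (152 + 30) = 7 / 182 = 3.8%. These are shares of days for an affected patient. The documents give neither the distribution of Safety Follow-up dates nor the event rate after stopping, so they cannot be turned into a count of missed events.

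**The case against.** The best defense is that section 9.4 is the section on the monitoring period, that 7.2.7 sends the reader to section 9 for complete details, and that 9.4 requires eCRF recording to day 30. On that view the notes are loose shorthand and nothing is lost. This stands in part: loss needs a site to follow the notes over 9.4 and a contact before day 30. It does not remove the conflict, because both rules are current text and no visit supports the longer one after an early switch.

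One can also argue that stopping at new therapy is deliberate, to keep the next drug's toxicity out of the tables. That is a legitimate design, and the protocol uses such a cut-off for following ongoing AEs. But the analysis window would then have to end there too, and it does not.

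A reader might infer more than the documents support:
- **That events are in fact under-counted.** A contact on days 30 to 37 loses nothing, and the number of earlier contacts is unknown.
- **That unrelated SAEs are lost.** Section 9.9 ties SAE reporting to the period in 9.4 and requires it whether or not the event is considered related.
- **That the on-treatment death count is wrong.** SAP section 4.7.4 classifies deaths by date, and survival follow-up supplies dates after new therapy. At most, the coded term in the summary by SOC and PT could be affected.
- **That crossover biases the comparison of arms.** Patients who cross over after the 7 to 28 day washout, or continue avapritinib, stay on study visits, and the SAP closes their main-period window the day before.
- **That the 1-week gap in exclusion criterion 4 shows fast switching.** It concerns therapy before the first study dose.

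**Conclusion.** The conflict is real and worth correcting, with a bounded consequence. A site that works from Table 2 notes w and x or section 7.1 can miss mainly non-serious AEs and concomitant medications between an early Safety Follow-up and day 30. The gap is 7 of 30 days at the early edge of the visit window and longer after an early switch to an off-study drug. As a share of a patient's whole TEAE window, a day-23 contact costs about 3% to 4% at the two longer assumed treatment durations and 12% after a single cycle. This assumes that the site stops at the visit and that the visit precedes day 30. How many patients meet both conditions, how many events are missed and whether the arms differ cannot be derived from the documents.

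**What to change.** - In Table 2 notes w and x and in section 7.1, replace the visit-based end with 30 days after the last dose of study drug. This matches sections 7.2.7 and 9.4 and the SAP.
- In section 4.1, section 7.8 and Table 2, set the Safety Follow-up contact at day 30 (+7 days), so that it cannot precede the end of the window. Treat any contact at the start of new antineoplastic therapy as additional.
- Flag AEs that start after new antineoplastic therapy so that they can be tabulated separately.

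Uncovered days then fall to zero for every patient contacted as scheduled, leaving only the SAP's own cut at crossover or extended treatment. The cost is protocol wording, the flag, and one extra call for patients who switch early; Table 2 note f and section 7.8 already allow a phone call. The downside is that some AEs from the next drug are recorded, which is why the flag is needed.
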